Data entry method: At enrollment, the RA will administer interviews using ACASI technology. Interview data will be directly entered on a lap top computer, which will be password protected, and will contain only participant study ID (no other identifying information). Additional data (e.g. urine drug test results) will be entered into a password-protected Redcap database by two separate, trained data entry staff, and discrepancies will be corrected by [name] based on source documents.

Data analysis plan: We will use mixed effects logistical regression models incorporating different correlation structures between study arms to account for clustering by group in the intervention arm. For the primary outcomes, abstinence will be the dependent variable and study condition will be the main independent variable. Covariates will include depressive symptoms and sociodemographic variables that are associated with the study condition in bivariate testing. For each secondary outcome, we will construct a separate mixed effects linear or logistic regression model with similar adjustments. In other exploratory analyses, we will determine whether changes in perceived social support or self-efficacy, depressive symptoms, or intensity of the intervention (i.e. # of group sessions attended) mediate the association between study condition and abstinence by using interaction terms with these variables and study condition. We will also determine whether sub-groups of patients (e.g. those with low perceived social support) benefit most from group participation.

QUALITY ASSURANCE

Validity and integrity: For interview data, participants will enter data directly into a laptop computer, but the RA will be available to answer any questions about interview. We will develop the computerized ACASI interviews so that there are limits on the potential responses that can be entered. The research assistant will also record and intervene if participants appear to be responding to questions too rapidly or in a mechanical way, which may indicate a problem with data integrity. Urine drug tests will be conducted at the community health center using commercially available rapid urine toxicology tests. To ensure validity and integrity of the urine samples, all urine samples will be collected by research staff. The RA will ensure that participants will not enter the private bathroom with jackets, purses, or any personal affects. The RA will stand outside of the bathroom to listen for possible tampering. In addition, research staff will ensure that the urine is warm (cold urine could indicate adulteration). Feasibility measures and written intervention materials will be collected using standardized paper forms by a trained research assistant. Protocol manuals and training of research assistants will include detailed discussion of the importance of recording reliable, valid data when observing group visits. [name] will review 25% of audio recordings from group visits to confirm fidelity to the intervention manual.

Accuracy and completeness: To ensure completeness of attendance at group visits, participants will receive a round-trip transit pass (worth \$5.50), which will facilitate transportation to and from the community health center. To ensure completeness of data collection, we will provide compensation (\$25) for each of the six research visits when interview and urine samples will be collected.

To ensure accuracy and completeness of interview data, we will program the ACASI interview such that participants will be required to answer each question before they can move on to the next question. If participants would like to skip a question, they will be able to inform the RA who will then advance the computer to the next question. Accuracy will be facilitated by using a touch screen computer (rather than a keyboard or mouse) which is likely to reduce participant errors. Data entry will not be required for interview data because participants directly enter their answers into the computer.

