Recruitment: We will review a register of BMT patients at the CHC who have consented to be contacted about research studies. We will contact patients who meet inclusion criteria and their providers. We will also extract data quarterly from electronic medical records to identify patients who have started buprenorphine treatment within the last 12 weeks. We will not contact patients directly, but instead, we will contact their primary care providers who will inform patients about the study and give the research team permission to contact patients. We will send potential participants letters from their PCP inviting them to participate in the study. Fliers describing the study will be posted at the CHC. The study will be described at staff meetings.

Randomization: A research assistant will contact and meet with eligible patients at the CHC to describe the study. At enrollment, written informed consent will be obtained, and forms to release medical records will be signed. Randomization will occur in blocks of 16 via a sealed envelope with allocation (G-BMT vs. TAU).

Screening Procedures: Potential participants who contact the study coordinator will be screened for inclusion and exclusion criteria. The study coordinator will also call potential study participants who are identified by PCPs or on the BMT register. The study coordinator will administer a three part screener by phone or in person. For patients referred to the study by their PCP, the study coordinator will check records to confirm: receipt of BMT for ≥ 12 weeks and documentation of illicit opioid use in the prior 6 months. The study coordinator will elicit oral informed consent based on a standard script and then ask seven screening questions to confirm receipt of buprenorphine, ongoing illicit opioid use, interest in group treatment, pregnancy, and other study inclusion/exclusion criteria. We will not be conducting pregnancy tests. To screen for unstable mental health conditions, the research coordinator will administer the suicidality, PTSD/violence risk, and psychosis modules from the MINI 6.0. If criteria for any of these conditions are met or if the research coordinator expresses concerns about group suitability, [name] will make a clinical assessment in person prior to study enrollment.

Research Visits: The research assistant will meet with all participants at enrollment and at 2, 4, 6, 8, 12, and 16 weeks

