following initiation of G-BMT or TAU. Research visits, which are separate from group medical visits or individual provider visits, will occur in a private room at the CHC and participants will receive \$25 compensation following completion of research activities. At each visit, computerized interviews and urine will be collected. Six months after enrollment, medical record data will be extracted for additional data collection.

Clinical Visits:

G-BMT intervention: The G-BMT intervention will begin with 8 weekly 90-minute group medical visits after a block of 8 participants has been randomized to the intervention arm. The anticipated protocol for G-BMT is described below. Urine drug tests will be collected at each group visit and will be used as a secondary study outcome and to modify management of addiction treatment as described.

The G-BMT intervention will include group medical visits where 8-10 patients simultaneously receive care from a multidisciplinary team of a generalist physician and a behavioral specialist (i.e. clinical social worker or psychologist). Patients will be expected to attend each 90 minute session, sign a confidentiality agreement, and will receive BMT prescriptions (one week supplies) only at the end of sessions (not in between visits). We anticipate that the G-BMT intervention will include: 1) BMT-related education, 2) instruction on self-management skills, 3) peer support, and 4) individual medical management.

Buprenorphine-related education: Topics will include buprenorphine pharmacology, neuroanatomic changes that occur with addiction, HIV risk reduction, and other topics related to opioid addiction. The generalist physician will deliver 15 minutes of information per visit.

Self-management skills: Empowering participants for self-management of their addiction will occur through an adapted cognitive behavioral intervention. Each visit will begin with completion of *self-assessment forms*, which will help participants set their own buprenorphine treatment goals, record progress toward goals, and privately report relapse. The behavioral specialist will provide 20-25 minutes of instruction at each visit.

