Treatment as usual: Participants randomized to TAU will continue to receive BMT from their PCPs based on a standardized BMT intensification protocol. Prior to the study, PCPs at the CHC will receive one hour of training on BMT intensification. The protocol will require that all BMT patients with persistent opioid abuse receive at least monthly visits with urine drug tests collected at each visit. For participants randomized to TAU, PCPs will receive an automated e-mail reminder about the following protocol. After one urine drug test is positive for opioids, PCPs will increase the frequency of visits to twice monthly with referral for behavioral counseling. After two consecutive positive tests, PCPs will increase visit frequency to weekly. After three consecutive positive tests, PCPs will refer to an addiction specialist or opioid treatment program. We will measure frequency of BMT visits, referral for behavioral counseling and referral to opioid treatment programs during the study. We will determine *observed intensity* of BMT (defined below) for exploratory analyses of treatment outcomes.

Participant tracking: To facilitate tracking participants over the 16 week follow-up period we will use tracking procedures that we developed to retain drug users in our previous research studies, in which we have had an 85% retention rate over 6-month follow-up. On Locator Forms, we will record information about: 1) participants' address and phone number; 2) contact information of participants' family members, friends, case managers, physician, pharmacy, and drug treatment program; and 3) locations where participants hang out.

Data sources and measures: A complete list of measures is listed in Table 1.

Urine Drug Testing: Research visits will include urine drug test collection, which will be used for the primary outcome (both G-BMT and TAU participants will have an equal number of research visits and urines). Urine drug tests collected during G-BMT and TAU medical visits (*clinical drug tests*) will be used for secondary outcomes.

Testing will include opiates, oxycodone, buprenorphine, methadone, cocaine, and benzodiazepines.

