What if participants continue to abuse opioids during the G-BMT intervention? RCTs demonstrate that methadone maintenance is more effective than BMT for severe opioid addiction. In real life settings though, methadone maintenance may be unavailable or unacceptable to opioid users. G-BMT will provide an option for treatment intensification in primary care that currently does not exist. We will ensure safety of research participants by only recruiting patients who already receive BMT from a waived physician, closely supervising participants during the G-BMT intervention, and facilitating referral to methadone maintenance treatment programs if participants have 3 consecutive urine drug tests that are positive for opioids and they are willing to transfer their care. We will also use an independent data safety monitoring committee to review study outcomes and adverse events every six months of the RCT.

IV. Data and Safety Monitoring Plan

Detailed data and safety monitoring plan. Because this study includes an RCT, we will utilize an internal independent data safety monitoring committee (DSMC).

Protocol Summary: We will conduct a 16-week RCT in primary care to preliminarily test the G-BMT intervention (8 weekly group visits) for efficacy, acceptability, and feasibility in comparison to treatment as usual (TAU) among BMT patients with persistent opioid abuse. Eighty participants with persistent opioid abuse during office-based BMT will receive treatment intensification in the G-BMT intervention or through TAU (i.e. increased frequency of visits with their primary care provider, referral for counseling, and/or referral to addiction specialist). Research visits for data collection will occur at baseline, 2, 4, 6, 8, 12, and 16 weeks after randomization and will include computer-based interviews and urine drug testing. We will also collect electronic medical record data. We will test **efficacy** by collecting interview, urine, and medical record data examining *abstinence* (primary outcome), *retention in treatment*, and *HIV-risk behaviors*, including drug-related and sexually-related risk factors. We will test **acceptability** by assessing patient and provider satisfaction following the trial. We will test **feasibility** by examining process measures, such as *medication and visit adherence* and fidelity to the intervention manual.

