Interview data will be collected via audio computer-assisted self-interview (ACASI) technology at baseline and during research visits 2, 4, 6, 8, 12, and 16 weeks following enrollment. *Urine samples* will be collected for drug testing at baseline and during research visits 2, 4, 6, 8, 12, and 16 weeks following enrollment. Urine drug tests will be conducted at the community health center using commercially available rapid urine drug test. At these research visits, the RA will ask subjects to provide a urine specimen in a private bathroom while the RA stands outside the door listening for tampering. Results of urine drug tests will be recorded on a standardized paper form only using the participants study ID and not other personal identifiers. *Feasibility* measures will be collected by the research assistant (RA) who will observe, time, and collect written intervention materials (e.g. self-assessment forms) from group visits. We plan to run 5 cycles of group visits, therefore, these field notes will be marked with the cycle number and group visit number but will not contain participant identifiers. *Written intervention materials* will be marked only with a study ID and transported directly to the research offices following weekly meetings between [name] (PI) and the research team. Materials will be stored in locked file cabinets. *Audio recordings* of each group visit and qualitative interviews will be collected by the RA using a digital audio-recording device. After each group visit or qualitative interview, audio recordings will be transferred to a single password protected encrypted computer and then erased from the recording device. Audio recordings will be uploaded to a secure internet portal for professional transcription and then will be transcribed with blinding of any references to personal identifiers.

Medical record data will be electronically extracting from Montefiore's centralized clinical database, and will include buprenorphine prescription data, and data on clinical visits (medical and counseling) and chronic health conditions. The electronic file will be created by Montefiore health technology staff, emailed to the PI in a password protected file, and saved on an encrypted password protected computer.

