Stress imposed on participants due to group participation: There will be a board certified physician and behavioral specialist at each group medical visit. Drs. [name] and [name] will also be available to intervene if participants express high levels of distress during group medical visits. Drs. [name] and [name] will review audio recordings of group sessions and have regular meetings with study clinicians to inquire about distress or conflict during group sessions.

Continuing BMT despite ongoing opioid abuse: We are selecting for a population with persistent opioid abuse, and these individuals may need a higher level of treatment intensity than can be offered in primary care settings.

Burden of attending an increased number of medical visits following intensification of BMT: Participants randomized to the G-BMT intervention will be expected to attend weekly group visits during the 8 week intervention. Participants randomized to the TAU arm will also likely be required to attend an increased number of medical visits, because PCPs will follow an intensification of BMT protocol that instructs them to increase visits to twice monthly or weekly if participants continue to abuse opioids. The increased number of visits could be burdensome and negatively affect adherence to buprenorphine treatment if participants missed medical visits and had lapses in their buprenorphine prescriptions.

Recruitment and informed consent: We will obtain informed consent for all participants of the RCT prior to collecting any information with personal identifiers (e.g. locator form or medical record release forms), administering the baseline ACASI interview, and randomization to an intervention arm. Informed consent will be obtained by the RA.

Protection against risk: We will institute the following processes to ensure confidentiality is maintained:

We will create a system that prevents linking sensitive material to participants' personal identifiers. We will have a "name-based" system and "ID-based" system that will remain all documents that have patient identifiers will be filed together. Some of these documents will have participants' signatures (e.g. consent forms) and others will have personal information (e.g. locator forms).

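### The research visits behind the primary outcome have three different week 0s and no stated TAU start, and records are extracted before the six-month retention window closes

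*Combined protocol and SAP*

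**What the plan says.** **Visit clock.** In section III, Research Visits, the visits at weeks 2, 4, 6, 8, 12 and 16 are timed "following initiation of G-BMT or TAU". The Protocol Summary in section IV has: "Research visits for data collection will occur at baseline, 2, 4, 6, 8, 12, and 16 weeks after randomization". Data acquisition and transmission, also in section IV, places interviews and urines "during research visits 2, 4, 6, 8, 12, and 16 weeks following enrollment".

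**Order of events.** The Randomization paragraph says "At enrollment, written informed consent will be obtained". Recruitment and informed consent puts consent before "administering the baseline ACASI interview, and randomization to an intervention arm". No interval between enrollment and randomization is given. On allocation, the plan says "Randomization will occur in blocks of 16 via a sealed envelope with allocation". Group visits start "after a block of 8 participants has been randomized to the intervention arm" (Clinical Visits, G-BMT intervention).

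**TAU.** Participants carry on with their own PCP. The only event particular to this arm is undated: "For participants randomized to TAU, PCPs will receive an automated e-mail reminder about the following protocol".

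**Outcomes.** The primary outcome combines urines at the week 8 and week 12 research visits with a 30-day self-report placed after the intervention ends. It cites Figure 1, which is not shown in the available text. The HIV-risk outcome equates week 8 with completion of G-BMT and week 16 with two months later. Retention is counted from study initiation, which is not defined, with a six-month window of weeks 24 to 28. Table 1 lists retention at weeks 0, 12 and 24. Medical records are extracted six months after enrollment (Research Visits).

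**The concern.** The Power Analysis section says that the more important goal is an effect size for designing a larger trial. That estimate needs one defined assessment time, the same in both arms. The primary-outcome urines are fixed only by week number, so their meaning depends on which week 0 staff use.

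On an enrollment clock, some G-BMT urines could be collected while the groups are still running. On the initiation clock that does not happen, but TAU then has no stated week 0, and no completion event on which to place its self-report.

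For retention, a participant whose only qualifying visit or active prescription arises after the extraction date could be wrongly counted as not retained. If only G-BMT waits between enrollment and initiation, that error would differ by arm.

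**Working it through.** **1. The plan's own figure.** Inputs from Power Analysis: 40 per arm, 10% control abstinence, ICC 0.01, 80% power, groups of 8. Alpha is not stated; I assume two-sided 0.05. The design effect is 1 + (8 − 1) × 0.01 = 1.07, so the effective size is 40 / 1.07 = 37.4 per arm. The pooled normal approximation then gives a minimum detectable rate of 37.1%, with power of 79.9% at 37%. The stated 37% reproduces. It contains no timing input, so this point leaves it unchanged.

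**2. Which clocks agree for G-BMT.** Let w be the wait in weeks from the clock's starting event to the first group visit.

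| Source | Week 0 | Fits week 8 as completion of G-BMT? |
|---|---|---|
| Research Visits | initiation | yes |
| HIV-risk outcome; Table 1 (fidelity checked in weeks 1–8) | implied first group visit | yes |
| Protocol Summary | randomization | yes if a block is randomized together; otherwise only when w is small |
| Data acquisition | enrollment | only when w is small |

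Take session 8 as held 7 weeks after session 1 (an assumption). On a clock that starts w weeks before the first group visit, session 8 falls at week w + 7. The week 8 visit precedes it when w > 1, and the week 12 visit when w > 5. That week 8 marks completion is stated for HIV risk behaviors; for the urines it is an inference.

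**3. Between-arm timing on the initiation clock.** If TAU initiation is taken as randomization (an inference), the week 12 urine falls 12 weeks after randomization in TAU and 12 + w weeks after it in G-BMT.

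**4. How long w might be (illustration only).** Assumptions not in the documents: even accrual, 8:8 allocation within blocks of 16, one-at-a-time randomization on the day of enrollment, and a group that starts as soon as eight are allocated.

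- Mean position of the eighth G-BMT participant in a block: 8 × 17 / 9 = 15.11. Mean position of all G-BMT participants: 8.5. Mean gap: 6.61 positions.
- Projected time table: 80 enrolled over 12 months, so spacing is 52 / 80 = 0.65 week. Mean wait = 6.61 × 0.65 = 4.3 weeks.
- At twice that speed the mean wait is 6.61 × 0.325 = 2.1 weeks; at four times, 6.61 × 0.1625 = 1.1 weeks. If a whole block is randomized together and the group starts at once, the wait after randomization is zero.

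With w = 4.3, step 3 gives 16.3 weeks in G-BMT against 12 in TAU.

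**5. Record extraction.** Six months is 365.25 / 2 / 7 = 26.1 weeks after enrollment. If study initiation comes w weeks after enrollment, the window runs from 24 + w to 28 + w weeks after enrollment. The pull precedes its close by 28 + w − 26.1 = 1.9 + w weeks: 1.9 weeks with no wait, and more with any wait. This step needs no accrual assumption.

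**The case against.** The strongest reply is that the operative text already gives a usable clock. Research Visits is the design section, and the outcome definitions and Table 1 fit it. The two competing phrases sit in a summary and a data-handling paragraph of the monitoring plan. TAU is continued care, so randomization is a natural start, and Figure 1 may show the timeline. Both arms are promised equal numbers of research visits and urines.

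Much of this stands. For G-BMT the conflict is with the enrollment wording, and with the randomization wording only under one-at-a-time allocation, which the Randomization paragraph does not settle. But equal numbers of visits do not give equal timing. Taking randomization as the TAU start makes the arms' visits fall at different times after randomization whenever G-BMT waits. Figure 1 could supply a TAU start, but it would not remove the conflicting wording elsewhere.

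Two stronger readings are tempting. A reader might infer that most primary-outcome urines in G-BMT would be collected mid-course. Under the step 4 assumptions, session 8 would indeed fall after week 8 for 81% and after week 12 for 44%. Those figures require staff to set aside the Research Visits clock, and at twice the accrual speed the 44% becomes 0%. The documents do not support them as an expectation.

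A reader might also infer that six-month retention is unascertainable for anyone whose window opens after the pull. That does not follow, because an active prescription counts, and one written before extraction may already run into the window. Table 1's week 24 entry is also covered by a six-month pull when there is no wait.

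**Conclusion.** The concern holds as a timing inconsistency that should be fixed. Three week 0s are stated for the visits that carry the primary outcome, retention adds an undefined fourth, and the available text names no TAU initiation event. Extraction at about 26 weeks precedes the close of the retention window by about 1.9 weeks even with no wait. With no wait, the loss is limited to participants whose only qualifying visit or active prescription arises between extraction and week 28.

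The sizes of w rest on assumed accrual and randomization mechanics and show only that the gap could be weeks rather than days. No bias in abstinence or retention, and no loss of power, can be computed from the documents. Confidence is medium, chiefly because Figure 1 is not visible and the mode of randomization is not stated.

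**What to change.** - Reconcile the Protocol Summary and Data acquisition wording to the Research Visits clock, with G-BMT week 0 at the first group visit.
- Name a TAU week 0 matched to it, for example the date of the same block's first group visit, or the participant's own randomization date if later. In the step 4 illustration, 16 − 15.11 = 0.89 TAU participants per block are randomized after the eighth G-BMT participant.
- Count the research visits, the post-intervention self-report and both retention windows from that week 0, and reconcile Table 1's week 24 retention entry with the 24–28 week window.
- Extract records no earlier than 28 weeks after week 0.
- Record the interval from randomization to week 0 by arm and report it with the results.

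The rule for when groups start need not change. When the groups and the PCP reminders begin is for the investigators to decide.

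The cost is wording, visit scheduling and a later electronic record pull. Some TAU visits would start later after randomization, possibly with the intensification protocol already under way. Averaging over all 12,870 possible allocations of a block in the step 4 illustration, the mean TAU interval to the matched week 0 is 6.80 × 0.65 = 4.4 weeks, close to the 4.3 weeks in G-BMT. N = 80 and the 37% detectable rate are unchanged.

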Provider Satisfaction: We will adapt a previously published questionnaire to assess acceptability of the intervention to participants' PCPs. Satisfaction will be measured in three areas: overall satisfaction with BMT, perceived effectiveness of BMT intensification and support for BMT at the CHC.¹⁰¹ We will add items for PCPs with patients randomized to the G-BMT intervention to assess satisfaction with communications with the G- BMT team and likelihood of referring patients to group-based BMT in the future.

Table 1. Timing and delivery of intervention and study measures

Measure	Study Instrument	Domain	Assessment Period (week)
Urine			
Opioid use	Observed urine	-	All [†]
Questionnaires			
Sociodemographic information	BHIVES Study ⁸²	-	0
HIV Risk Behaviors	AIDS risk inventory ⁹³	-	0, 8, 16
Self-reported drug use	Addiction Severity Index ⁹⁴	-	All
Depression	CES-D ⁹⁵	-	0, 8, 16
Self-efficacy	DTCQ-8 ⁹⁶	Self-efficacy	0, 8, 12, 16
Social Support	MSPSS ⁹⁷	Outcome Expectation	0, 8, 12, 16
Buprenorphine Knowledge	10 item questionnaire	Knowledge	0, 8, 16
Quality of Life	SF-12 ⁹⁸	-	0, 8, 16
Group cohesion*	GCQ-S ⁹⁹	-	2, 4, 8
Medical Records			
Medical Visits	-	-	1-16
Buprenorphine prescriptions	-	-	1-16
Referrals	-	-	1-16
Opioid use	Clinical urine		1-8
Retention in care	-	-	0, 12, 24
Intervention Materials			
Chronic Health Conditions	-	-	0
Self-assessment forms	Check-list	Goals	1-8
Intervention fidelity	Check-list	-	1-8
Post-intervention Questionnaires			
Patient satisfaction	PCBSS ¹⁰⁰	Barriers and Facilitators	8
Provider satisfaction	5 item questionnaire ¹⁰¹	-	8
Qualitative Interviews*	Interview Guide		8

*only collected for intervention arm; [†]Study visits (2,4,6,8,12,16 weeks) CES-D = Center for Epidemiologic Studies Depression Scale; DTCQ-8 = Drug-Taking Confidence Questionnaire, 8 item version; MSPSS = Multidimensional Scale of Perceived Social Support; SF-12 = SF-12 Health Survey; GCQ-S = Group Climate Questionnaire – Short Form; PCBSS = Primary Care Buprenorphine Satisfaction Scale

Analysis:

Main outcome variables:

Primary outcome (efficacy): we will use a dichotomous measure (yes/no) of *opioid abstinence* based on 30-day self-reported opioid use following completion of the intervention and the results of urine drug tests (opiates, methadone, oxycodone) at the 8 and 12 week research visits (see Figure 1). Missing urine drug tests will be considered to be positive for opioids.

Secondary outcomes (efficacy):

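### Clinical urine tests are named as a secondary outcome, but the testing schedule differs by arm and in TAU depends on earlier results, so most simple summaries can differ between arms under identical drug use

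*Combined protocol and SAP*

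**What the plan says.** Under Clinical Visits, the G-BMT description states: "Urine drug tests will be collected at each group visit and will be used as a secondary study outcome". Under Data sources and measures, the Urine Drug Testing paragraph says that clinical tests from G-BMT and TAU visits "will be used for secondary outcomes". Table 1 has an opioid-use row for clinical urine in weeks 1-8, without the asterisk that marks measures limited to the intervention arm. The itemised secondary efficacy outcomes, both under Main outcome variables and under Outcome Measures in the Data and Safety Monitoring Plan, list only retention and HIV risk behaviors.

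The two testing schedules are:

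- **G-BMT:** "The G-BMT intervention will begin with 8 weekly 90-minute group medical visits", with a urine at each.
- **TAU:** patients with persistent opioid abuse "receive at least monthly visits with urine drug tests collected at each visit". Then: "After one urine drug test is positive for opioids, PCPs will increase the frequency of visits to twice monthly". Then: "After two consecutive positive tests, PCPs will increase visit frequency to weekly". Finally: "After three consecutive positive tests, PCPs will refer to an addiction specialist or opioid treatment program".

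Equal numbers of urines by arm are assured only for the research visits (weeks 2, 4, 6, 8, 12 and 16 after baseline). The written primary outcome uses those taken "at the 8 and 12 week research visits".

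The Analysis section promises a separate mixed linear or logistic model for each secondary outcome. It names clustering by group and by PCP. The Data analysis plan names clustering by group only. Neither mentions repeated tests within a participant, the number of tests, or a common set of test weeks.

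**The concern.** In TAU the number of tests a patient has depends on the results of earlier tests, while in G-BMT it is fixed by the calendar. Three effects follow.

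- More tests give more chances of a positive. Any-positive and number of positives therefore count against G-BMT.
- In TAU, heavier users are tested more often and supply a larger share of the tests. When patients differ in risk, the pooled percent positive is inflated in TAU and favours G-BMT.
- In TAU, an early negative is followed by few tests and leaves a low personal percentage. An early positive is followed by further tests that dilute it. The mean of person-level percentages is therefore lower in TAU.

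Because no summary is fixed, the apparent direction of a between-arm difference could turn on a choice made after the data are seen. Power Analysis says the more important aim is an effect size for a larger trial, and a schedule-driven difference in a drug-use outcome could mislead that design work.

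**Working it through.** **The plan's own figure.** No figure is given for the clinical-urine outcome. The only design figure, a detectable abstinence rate of 37%, concerns the primary outcome. It reproduces: design effect 1 + (8 - 1) x 0.01 = 1.07; effective n 40 / 1.07 = 37.4 per arm; control rate 10%, 80% power, two-sided alpha 0.05 (assumed) gives 37.1%. It does not bear on this point, but the 10% control rate helps to choose a scenario below.

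**Inputs from the documents.** G-BMT: 8 weekly tests. TAU: 4-weekly, 2-weekly after one positive, weekly after two consecutive positives. Window: weeks 1-8 (Table 1).

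**Assumptions.** Identical use in both arms; 80% attendance; each patient has a stable weekly probability p of a positive test, varying between patients; first TAU visit at week 1 or week 4; no loss of tests after referral. Three distributions of p are used: Beta(0.6, 1.4), mean 0.30; uniform, mean 0.50; Beta(3, 1), mean 0.75.

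**Simplest case.** With full attendance and p = 0.2 for everyone, any positive is 1 - 0.8^8 = 83% in G-BMT and 1 - 0.8^2 = 36% in TAU. Escalation cannot change the TAU figure, because it starts only after the first positive. The mean number of positives is 1.60 versus 0.45.

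**Any positive with varying risk.** The probability is 1 - E[(1 - 0.8p)^k], with k = 8 in G-BMT and k = 2 in TAU.

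- Uniform: E = [1 - 0.2^(k+1)] / [0.8(k+1)]. For k = 8 this is 1/7.2 = 0.139, giving 86%. For k = 2 it is 0.992/2.4 = 0.413, giving 59%.
- Mean 0.30 (E[p^2] = 0.16): TAU is 1.6 x 0.30 - 0.64 x 0.16 = 38%. G-BMT, by numerical integration, is 66%.
- Mean 0.75 (E[p^2] = 0.60): TAU is 1.6 x 0.75 - 0.64 x 0.60 = 82%. G-BMT is 99%. If TAU starts two-weekly (k = 4), TAU is 94%.

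**Pooled percent positive, by simulation of the same schedules.**

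| Mean positivity | Any positive, G-BMT vs TAU | Pooled percent positive, G-BMT vs TAU |
|---|---|---|
| 30% | 66% vs 38% | 30% vs 34-39% |
| 50% (uniform) | 86% vs 59% | 50% vs 55-59% |
| 75% | 99% vs 82% (94% if TAU starts two-weekly) | 75% vs 76-79% (low end from a two-weekly start) |

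In the uniform case, tests per person are 8 x 0.8 = 6.4 versus 2.1-3.1, and the mean person-level percentage is 50% versus 43-47%. If TAU testing stops after three consecutive positives, the any-positive gap is unchanged and the pooled figure becomes 50% versus 53-55%.

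**Which scenario fits the plan.** The chance of two negative urines is 1 - 2E[p] + E[p^2]: 1 - 0.60 + 0.16 = 56% at mean 0.30; 1 - 1 + 1/3 = 33% for uniform; 1 - 1.50 + 0.60 = 10% at mean 0.75. The last matches the plan's 10% control abstinence. Self-report and the missing-as-positive rule also lower abstinence, so lower positivity is not excluded.

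**Where the distortion vanishes or nearly so.** If everyone has the same independent risk, the pooled share is equal by arm (20% vs 20% at p = 0.2; 30% vs 30% at p = 0.3). A test-level logistic mixed model with a participant random effect gave arm odds ratios of 0.98-1.07 in simulations with mean positivity of about 31%, 50% and 73%, where pooled percentages differed by 3-10 points. That result assumes stable risk and no dropout after referral.

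**The case against.** The case on the other side has four parts.

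1. **No between-arm endpoint is defined, so any bias is conditional.** Table 2 lists the number of urine tests collected among feasibility measures that serve as secondary outcomes, and the G-BMT statement could be read that way. This is possible but not the natural reading: Table 1 labels clinical urine as opioid use, and the Urine Drug Testing paragraph names both arms. At the least, the status of these tests must be reconciled.

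2. **A mixed model is already planned and could absorb result-driven testing.** This stands in part. Escalation depends on observed results, so a participant random effect would remove most of the distortion. The plan names group and PCP as clusters, not the participant.

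3. **The gap may be smaller than the low-positivity scenarios show.** This stands. The TAU frequency is a minimum, and the Background describes twice-monthly or weekly visits as common for patients who continue to use. At high positivity or with denser TAU testing, any-positive narrows to 99% versus 94% and the pooled share is nearly equal.

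4. **The main comparison is protected.** This stands: the primary outcome rests on research urines, equal in number by arm.

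A reader might infer that every usual summary of the clinical urines is distorted, or that the trial's efficacy result is compromised. The documents support neither. The pooled share is undistorted under equal, independent risk, a suitable test-level model largely corrects the problem, and the primary outcome uses other urines.

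**Conclusion.** The point holds as a recommended change to a secondary outcome. The plan commits clinical urines from both arms to secondary outcomes, tests the arms on different schedules, lets TAU frequency depend on results, and specifies nothing to account for this. Under identical use, the any-positive gap ranges from 28 percentage points (66% vs 38%) to 5 (99% vs 94%), against G-BMT. The pooled gap ranges from about 1 to 9 points in favour of G-BMT. These sizes rest on assumed attendance, positivity and TAU start. That the direction depends on the summary follows from the two schedules, provided patients differ in risk.

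**What to change.** Define the between-arm secondary drug-use outcome as the research urines at weeks 2, 4, 6, 8, 12 and 16, analysed in a mixed logistic model with a participant random effect added to the planned clustering terms. State whether the missing-as-positive rule, now written for the primary outcome, also applies here. Amend the G-BMT description, the Urine Drug Testing paragraph and both lists of secondary outcomes so that they agree.

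Use clinical urines descriptively. If they are compared between arms, do so only with a model that accounts for repeated, result-dependent testing within participant.

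The cost is analysis wording. The research urines are already planned on the same schedule in both arms, so no visit, test or clinical rule changes.
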